5.1.2.4. Study-Specific Definitions

Exposure Day

One ED is defined as a 24-hour period in which a patient receives 1 or more doses of rFVIIIIFc, with the time of the first injection of rFVIIIIFc defined as the start of the ED.

Bleeding Episode

A bleeding episode is defined as follows: A bleeding episode starts from the first sign of bleeding and ends no more than 72 hours after the last injection to treat the bleeding, within which any symptoms of bleeding at the same location, injections ≤ 72 hours apart, are considered the same bleeding episode. Any injection to treat the bleeding episode, taken >72 hours after the preceding one, will be considered the first injection to treat a new bleeding episode in the same location. Any bleeding at a different location is considered a separate bleeding episode, regardless of the time from the last injection.

Spontaneous Bleeding Episode

Bleeding episodes are classified as spontaneous if a parent/caregiver records a bleeding event when there is no known contributing factor such as a definite trauma or antecedent “strenuous” activity. The determination of “strenuous” is at the discretion of the Investigator, and the parent/caregiver/patient will be instructed on this by the Investigator.

Traumatic Bleeding Episode

Bleeding episodes are classified as traumatic if the parent/caregiver records a bleeding episode even when there is a known or believed reason for the bleeding. For example, if a patient exercises strenuously and then has a bleeding episode in the absence of any obvious injury, the bleeding episode will still be recorded as traumatic. Target joint bleeding episodes can be traumatic if a known action leads to bleeding into the joint. The Investigator considers whether events resulting in a traumatic bleeding episode qualify as AEs and reports as such.

High and Low Titer Positive Inhibitors

A positive inhibitor test result is defined as an inhibitor test result of ≥ 0.60 BU/mL that is confirmed by a second test result of ≥ 0.60 BU/mL from a separate sample, drawn at least 2 weeks after the date when the original sample was drawn. Both tests must be performed by the central laboratory using the Nijmegen-modified Bethesda assay and the date of the inhibitor is the date of the sample with the first positive test result which was subsequently confirmed.

- A positive low titer inhibitor is defined as an inhibitor test and confirmatory test, both with results of ≥ 0.60 and < 5.00 BU/mL.
- A positive high titer inhibitor is defined as an inhibitor test and confirmatory test, both with results of ≥ 5.00 BU/mL.

Patients with discordant inhibitor test results (initial low titer result followed by high titer result or initial high titer result followed by low titer result) should have repeat inhibitor testing performed by the central laboratory from third separate sample, drawn at least 2 weeks after the previous sample.

- If 2 of 3 test results are < 5.00 BU/mL, the inhibitor is considered low titer.
- If 2 of 3 test results are ≥ 5.00 BU/mL, the inhibitor is considered high titer.

In either case, the date of the inhibitor is the date of the sample with the first positive test result.

	Statistical Analysis Plan	Final v1.0
---	----------------------------------	-------------------

If, as per the algorithm above, a patient is initially classified as having a low titer inhibitor which subsequently becomes high titer using the same rules, this patient may be re-classified as follows:

- If the patient’s inhibitor becomes high titer without a significant increase in dose, defined as a dose that more than doubles between the time of development of the low titer and high titer inhibitors, then the patient should be considered high titer for the entire inhibitor period
- If the patient’s inhibitor becomes high titer after a significant increase in dose, defined as a dose that more than doubles, or after the patient commences ITI, then the patient should be considered low titer for the entire inhibitor period

All analysis of, and derivations based upon, inhibitor test results are performed using the Nijmegen Inhibitor Fc assay test.

5.1.2.5. Subgroup Definitions

Surgery Subgroup

The Surgery Subgroup is defined as all patients who have undergone major surgery after first dose of study drug. This set will be described in the disposition table and all analyses and listings of major surgeries will be presented for this population.

Inhibitor Subgroup

Patients developing a positive inhibitor after exposure to rFVIII Fc will be included in Inhibitor Subgroup. Within this subgroup, there are several further classifications:

1. Patients with high-titer inhibitors, defined as in Section 5.1.2.4
2. Patients with low-titer inhibitors, defined as Section 5.1.2.4, that meet the below clinically meaningful criteria
3. Patients with low-titer inhibitors that do not meet the below clinically meaningful criteria

The delineation of clinically meaningful will be performed on a case-by-case basis via medical adjudication just prior to the interim or final analyses, based upon the data available for the analysis. This assessment will take account of relevant clinical factors, including but not limited to:

- Entry to the ITI sub-study
- Any bypassing or immunomodulatory agents received up to 4 weeks before inhibitor development and any time after
- Withdrawal from the study due to complications assessed as related to inhibitor development
- Any SAE of a bleeding event up to 4 weeks before inhibitor development or any time after

- A pattern of non-serious treated bleeding events which require a change in study drug (rFVIII Fc) regimen

Patients who undergo ITI will be part of the ITI Analysis Set (see Section 4.4). By definition, all high-titer inhibitors are clinically meaningful, as patients with high-titer inhibitors must either enter the ITI sub-study or withdraw.

5.1.2.6. End of Study

The end of the study (EOS) will occur after at least 90 patients have reached at least 50 EDs with rFVIII Fc. Once this milestone has been achieved, all ongoing study patients will return to the study center for their final visits.

5.1.3. Pooling Sites for Analysis

All sites will be pooled and reported together for analysis.

5.1.4. Handling of Missing Data

Aside from the following, no imputation of study data will be performed.

The occurrence of a new bleeding episode will be imputed if >72 hours lapse between 2 consecutive injections administered to treat bleeding. Details are provided in Section 7.4.1.

For the analysis of AEs and concomitant medications/procedures, if the stop/start date of an AE/concomitant medication is missing or partial, the corresponding study day will be left blank. However, inferences will be made from the partial and missing dates to classify medications as prior and/or concomitant and AEs as treatment emergent (or not). These inferences are described in Sections 6.4.1 and 9.3.1, respectively.

For the ITI subset, determination of response requires baseline IR. If this is missing, an absolute value is employed. Further details can be found in Section 7.4.9.

5.2. Treatment Regimens for Analysis

For the purpose of analysis, the treatment regimen means the actual treatment regimen(s) that the patient follows over the course of the study (i.e., not necessarily the regimen they started on). For example, a patient who starts the study on the episodic regimen and switches to a prophylactic regimen will appear in the summaries of both the episodic and the prophylactic regimens based on the time he spent in the respective regimens.

5.2.1. Start Date and Time of the First Treatment Regimen

The start date and time of the first treatment regimen is defined as either:

- The date and time of the first rFVIII Fc dose for patients beginning on a prophylactic treatment regimen, as per the treatment assignment eCRF data
- The date and time 120 hours after the date and time of the baseline PK dose, for patients beginning on an episodic treatment regimen, as per the treatment assignment eCRF data

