## 7. STUDY DESIGN

### 7.1. Study Overview

This is an open-label, single-arm, multicenter study evaluating the safety and efficacy of rFVIIIc in previously untreated pediatric subjects with severe hemophilia A when used according to local standard of care. Following the confirmation of eligibility, the Investigator has the option to treat eligible subjects episodically (on-demand) prior to initiating a prophylaxis regimen. The duration of episodic treatment is at the Investigator's discretion, in accordance with local standard of care. At least 90 previously untreated subjects are planned to complete the study after reaching at least 50 EDs with rFVIIIc.

Baseline IR may be conducted along with other baseline assessments on the same day as screening, once the subject has been enrolled, or as part of a separate baseline IR visit, as long as the subject has not yet had more than 3 doses of rFVIIIc.

Subjects with a documented plasma FVIII activity of <1% may be enrolled on the basis of local laboratory results and may receive study drug after samples for factor VIII activity level and inhibitors, for testing at the central laboratory, have been obtained. However, any such subject must be withdrawn if the central laboratory screening results indicate factor VIII activity level  $\geq 1\%$  or a positive inhibitor.

Major and minor surgery are allowed during the study (Section 10.2.8).

ITI with rFVIIIc is allowed during the study for those subjects developing, after exposure to rFVIIIc study drug, a positive high titer inhibitor ( $\geq 5.00$  BU/mL) or a positive low titer inhibitor ( $\geq 0.60$  and  $< 5.00$  BU/mL) with poorly controlled bleeding despite increased rFVIIIc doses or requiring bypassing agents to treat bleeding (Section 10.2.5.2).

Because of the risk of allergic reactions with FVIII concentrates, the initial administrations of rFVIIIc should be performed under medical observation where proper medical care for allergic reactions could be provided. The first injection of rFVIIIc study drug after the Screening Visit must be administered by the Investigator or a qualified delegate. Thereafter, study treatment may be administered by a parent/caregiver or by a qualified medical professional under the direction of the Investigator. Study treatment may also be injected in the hospital during surgery or during hospitalization due to major bleeding.

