### **16.2. Efficacy**

#### **16.2.1. Analysis Population**

Subjects who receive at least 1 dose of rFVIIIhFc will be included in the Full Analysis Set (FAS). Efficacy analyses will be based on the FAS, including the data collected on or after the time of the first injection of rFVIIIhFc study drug.

Subjects developing a confirmed positive inhibitor test after exposure to rFVIIIhFc (the Inhibitor Subgroup) will have their efficacy data included up to the time of the last negative inhibitor test; efficacy data collected after the time of the last negative inhibitor test will be summarized separately.

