5.4.2. Efficacy Period

The efficacy period will be used for the evaluation of efficacy and health outcome endpoints. For a patient to have an evaluable efficacy period over the duration of study, he must have at least 1 day of treatment for an episodic regimen or at least 2 prophylactic injections for prophylactic regimens.

The start and end, and the total duration of the efficacy period for a given treatment regimen is the same as the start and end, and the total duration of that treatment regimen defined in Section 5.2.4 with the exceptions described in the following two subsections. The start of the efficacy period for each patient is the start of their first treatment regimen and the end is the end of their last.

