5.4.4. Safety Period

The overall safety period is defined as beginning at the first dose of study medication rFVIII Fc. For patients who are subsequently enrolled, the safety period ends on the date of the Final Safety Follow-up Visit (by telephone or in person), 7 to 14 days after the last dose of rFVIII Fc. For patients who fail screening, this period ends on the date that this is confirmed.

The safety period on a specific treatment regimen is as described in Section 5.2 except that the end of the patient's last treatment regimen is the end of their safety period.

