7. EFFICACY ANALYSIS

7.1. General Efficacy Principles

Efficacy analyses will be based on the Full Analysis Set and unless otherwise specified, presented by the treatment regimen groups described in Section 5.1.1.1.

Additionally, the general efficacy and surgical/rehabilitation periods are defined in Section 5.4. Data on bleeding and rFVIIIFc consumption will be based on the efficacy period; surgical evaluations will be based on the surgical/rehabilitation period.

Analysis of efficacy endpoints that are visit-based will include data from all study visits whether or not in the efficacy period, unless that visit is coincidental with a surgical/rehabilitation period for a major surgery, in which case it would be excluded.

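### For children who start on episodic treatment, the SAP starts the first regimen 120 h after the baseline PK dose, so earlier treated bleeds leave the ABR and early AEs fall in no regimen column

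*SAP*

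**What the plan says.** SAP 5.2.1 gives two starts for the first regimen. The first rFVIIIFc dose applies "for patients beginning on a prophylactic treatment regimen, as per the treatment assignment eCRF data". For episodic starters the start is "The date and time 120 hours after the date and time of the baseline PK dose".

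Three other parts of the SAP depend on this:

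- **Efficacy period (SAP 5.4.2):** "The start of the efficacy period for each patient is the start of their first treatment regimen".
- **Bleeding and consumption (SAP 7.1):** these data, including "consumption will be based on the efficacy period; surgical evaluations will be based on the surgical/rehabilitation period". SAP 7.4.3 and 6.6.1.4 use days in the efficacy period as the denominator for ABR and annualized consumption.
- **Safety (SAP 5.4.4):** "The overall safety period is defined as beginning at the first dose of study medication", but "The safety period on a specific treatment regimen is as described in Section 5.2".

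The protocol allows the baseline recovery dose to come after other doses, "as long as the subject has not yet had more than 3 doses" (7.1). Protocol 16.2.1 bases efficacy on the FAS, "including the data collected on or after the time of the first injection". Protocol 10.2.2, repeated in SAP 3.1.5.1, starts episodic treatment once eligibility is confirmed. Protocol 16.2.2 leaves the definition of the efficacy period to the SAP. SAP 10, which lists the major differences from the protocol, does not mention the 120 h rule, and neither document gives a reason for it.

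**The concern.** A child on episodic treatment may be dosed for bleeds before the baseline PK dose. Protocol 10.2.4.1.4 asks for bleeds treated before the diary is issued to be recorded in the eCRF, with dose and response. The trial therefore collects these bleeds, and the SAP's period definition then removes them from ABR, from annualized consumption, and from the response and injections-to-resolve summaries that rest on the efficacy period. SAP 5.1.1 gives efficacy tables no total column, and the whole-patient efficacy period starts at the same point, so no other ABR table recovers them. Protocol 16.2.3 asks for ABR both by regimen and overall.

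Prophylaxis is expected to begin by about the third joint bleed (protocol 10.2.2). Episodic phases may therefore hold few bleeds, and losing one can matter.

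On safety, the days after first exposure are when protocol 7.1 and 10.1 call for observation for allergic reactions. AEs in those days are credited to the prophylaxis column for prophylaxis starters, but to no regimen column for episodic starters.

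**Working it through.** The documents state no figure to reproduce. The check traces the definitions and then illustrates the size. Episodic lengths and bleed counts below are assumptions, because the documents give none.

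**1. Excluded time.** 120 / 24 = 5.0 days after the PK dose, plus the interval from first dose to PK dose. If the PK dose is the first dose, the loss is 5 / 30 = 16.7% of a 30-day phase, 5 / 90 = 5.6% of a 90-day phase and 5 / 365 = 1.4% of a 365-day phase.

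**2. ABR with the PK dose as first dose.** ABR = bleeds / days × 365.25 (SAP 7.4.3). From first dose, over T days, all bleeds count. Under the SAP, only bleeds after 120 h count, over T − 5 days.

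| T (days) | 1 early, 1 later bleed: first dose / SAP | 0 early, 1 later bleed: first dose / SAP |
|---|---|---|
| 30 | 24.35 / 14.61 | 12.18 / 14.61 |
| 90 | 8.12 / 4.30 | 4.06 / 4.30 |
| 180 | 4.06 / 2.09 | 2.03 / 2.09 |
| 365 | 2.00 / 1.01 | 1.00 / 1.01 |

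For example, at T = 90: 2 / 90 × 365.25 = 8.12 and 1 / 85 × 365.25 = 4.30.

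**3. ABR with a later PK dose.** Take T = 90 with one bleed before the mark and one after. From first dose the ABR is 8.12. With the PK dose on day d, the SAP gives 1 / (90 − d − 5) × 365.25:

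- d = 14: 1 / 71 × 365.25 = 5.14
- d = 30: 1 / 55 × 365.25 = 6.64
- d = 60: 1 / 25 × 365.25 = 14.61

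The shift can therefore go either way, since numerator and denominator are both cut.

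**4. Is 120 h a plausible washout?** Inputs are the 25 IU/kg baseline dose (protocol 10.2.1.1) and, from protocol Table 1 for age under 6, a half-life of 12.28 h (95% CI 10.99 to 13.72) and recovery of 1.901 IU/dL per IU/kg (1.785 to 2.024). Assume mono-exponential decline from zero baseline.

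- Half-lives elapsed: 120 / 12.28 = 9.8 (8.7 to 10.9 over the CI).
- Peak: 25 × 1.901 = 47.5 IU/dL.
- Time to 1 IU/dL: 12.28 × log2(47.5) ≈ 68 h (60 to 78 h over the CIs).
- Activity at 120 h: 47.5 × 2^(−9.77) ≈ 0.05 IU/dL (0.02 to 0.12).

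The 5 days would clear the PK dose. They say nothing about time or bleeds before it.

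**5. Undefined cases.** An episodic starter with no baseline PK dose has no start time. Protocol 10.2.7.4.1 conditions one definition on having a baseline recovery value, and a child who passes the three-dose limit can no longer have the visit. Separately, SAP 5.2.3 ends the episodic regimen one minute before the first prophylactic dose. If that dose falls less than 120 h after the PK dose, the end precedes the start. At an assumed 72 h, the duration is 72 h − 1 min − 120 h = −48 h 1 min.

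**The case against.** A reader might infer that the SAP contradicts the protocol. The documents do not support that. Protocol 16.2.1 sets the data scope of the FAS, but 16.2.2 hands the efficacy period to the SAP and bases bleeding and consumption on it. Protocol 16.5 asks only for overall safety summaries unless the SAP says otherwise, so the regimen columns are the SAP's own addition.

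Nor are early AEs lost. The overall safety period starts at first dose, safety tables have a total column (SAP 5.1.1), SAP 6.6 keeps the time around the PK dose in the safety analyses, inhibitor-subgroup tables use the entire period (SAP 5.1.1.2), and all AEs are listed. Only attribution to a regimen fails.

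The asymmetry also has a plausible reason. The PK dose is not given to prevent or treat bleeding, so factor-covered days would otherwise count as on-demand time. Prophylaxis starters are meant to be covered and need no lag. In addition, a clock started at a bleed-triggered first dose counts that bleed with no time at risk before it, which pulls ABR upward. SAP 5.1.2.2 expects the baseline visit as soon as practicable, and several injections can belong to one bleeding episode, so three prior doses need not mean three lost bleeds.

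All of this stands. It does not explain dropping bleeds treated before the PK dose, starting regimen-level safety late, or leaving some patients without a valid start.

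**Conclusion.** The point holds as an unexplained narrowing of protocol 16.2.1 that SAP 10 does not list. For episodic starters, treated bleeds before the 120 h mark and the matching time leave the episodic and whole-patient ABR, consumption and other efficacy-period summaries. AEs in that window have no regimen column.

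The size depends on when the PK dose is given and how long episodic treatment lasts, and the documents give neither. In the illustrations the SAP's ABR ranges from about half the first-dose value (4.30 against 8.12) to well above it (14.61 against 8.12). It would be wrong to infer that the rule always understates ABR. It would also be wrong to say that a child without a PK dose loses all episodic time: that case is undefined, not excluded.

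The primary inhibitor analysis (SAP 9.4.3.2), exposure-day counts (SAP 6.6.1.1) and visit-based endpoints (SAP 7.1) are unaffected. The raw bleed count in SAP 7.4.2 is described as covering all episodes and may also be spared, although SAP 7.1 leaves this unclear. The study is descriptive, so no test is at stake, but reported secondary results change.

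**What to change.** 1. **Safety.** Start the regimen-specific safety period in SAP 5.4.4 at the first rFVIIIFc dose for both regimens.
2. **Efficacy.** Choose one:
   - Start the episodic regimen at the first rFVIIIFc dose. PK doses are already excluded from consumption (SAP 6.6).
   - If a PK washout is intended, exclude only the 120 h after the PK dose and keep earlier episodic time and bleeds. State the reason, list the rule in SAP 10, and report ABR from first dose as a sensitivity analysis.
3. **Gaps.** Add a rule for an episodic starter with no baseline PK dose and for a regimen change within 120 h of it. Starting at first dose closes both.

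The cost is a few lines of text and derivation code. Episodic ABR may rise, partly because a bleed that triggers the first dose is counted with no time at risk before it. The first option also counts days covered by the PK dose as episodic time. The report should say so.

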5.2.2. End Date and Time of the Last Treatment Regimen

The end of the last treatment regimen will be either:

- The date and time of the last rFVIII Fc dose for patients whose last treatment regimen was prophylaxis, ITI, or if they ended the study in a surgical/rehabilitation period
- At 23:59 on the day of the last non-safety follow-up study visit for patients whose last treatment regimen was episodic.

5.2.3. Treatment Regimen Changes

In the following sections, new treatment regimen refers to the regimen to which the patient has changed, and the previous treatment regimen refers to the regimen immediately before the new treatment regimen. The start date and time of the new treatment regimen and the end date and time of the previous treatment regimen are defined in the following scenarios:

- From the episodic regimen to a prophylactic regimen: The prophylactic regimen starts at the date and time of the first prophylactic dose in the prophylactic regimen. The episodic regimen ends 1 minute before that. If the time of the first prophylactic dose in the prophylactic regimen is not available, the prophylactic regimen will start at 00:01 on the day of the first prophylactic dose in the prophylactic regimen, and the episodic regimen will end at 23:59 on the day prior to that.
- From the episodic regimen to an ITI regimen: The ITI regimen starts at the date and time of the first ITI dose in the ITI regimen. The episodic regimen ends 1 minute before that. If the time of the first ITI dose in the ITI regimen is not available, the ITI regimen will start at 00:01 on the day of the first ITI dose in the ITI regimen, and the episodic regimen will end at 23:59 on the day prior to that.
- From a prophylactic regimen to the ITI regimen: If there is no prophylactic dose on the day of the treatment regimen change recorded in the eCRF, the ITI regimen starts at 00:01 on the day of treatment regimen change, and the prophylactic regimen ends at 23:59 on the day prior to the day of treatment regimen change. If there is a prophylactic dose on the day of treatment regimen change, the ITI regimen starts 1 minute after that prophylactic dose, and the prophylactic regimen ends on the date and time of that prophylactic dose.
- From a ITI regimen to a prophylactic regimen (tapering): If there is no ITI dose on the day of treatment regimen change recorded in the eCRF, the prophylactic regimen starts at 00:01 on the day of treatment regimen change, and the ITI regimen ends at 23:59 on the day prior to the day of treatment regimen change. If there is an ITI dose on the day of treatment regimen change, the prophylactic regimen starts 1 minute after that dose, and the ITI regimen ends on the date and time of that dose.

